## 5. STUDY TREATMENT

### 5.1. Investigational Products Administered

The term “investigational product (IP)” refers to the mRNA-1283, mRNA-1283.211, mRNA-1273, and mRNA-1283.529 vaccine candidates and mRNA-1273 vaccine administered in this study.

The mRNA-1283 Drug Product is an LNP dispersion containing a single mRNA sequence that encodes a protein made up of 2 segments of the SARS-CoV-2 S protein: the NTD and RBD, which are linked together with a 7-amino-acid flexible linker. These three proteins (NTD, RBD, and linker) are attached to a 23-amino-acid transmembrane domain from influenza HATM via a 5-amino-acid flexible linker. This entire protein makes up the NTD-RBD-HATM antigen and is encoded by mRNA-1283. The mRNA is combined in a mixture of 4 lipids common to the Sponsor’s mRNA vaccine platform: SM-102, cholesterol, 1,2-distearoyl-sn-glycero-3-phosphocholine (DSPC), and 1 monomethoxypolyethyleneglycol-2,3-dimyristylglycerol with polyethylene glycol of average molecular weight 2000 (PEG-2000-DMG).

mRNA-1283 is provided as a sterile liquid for injection, as a white to off-white dispersion in appearance, at a concentration of 0.4 mg/mL in 20 mM Tris buffer containing 87 mg/mL sucrose and 10.7 mM sodium acetate, at pH 7.5. mRNA-1283 is packaged in 2R US Pharmacopeia (USP) Type I borosilicate glass vials with a PLASCAP® vial seal containing a 13-mm FluroTec-coated plug stopper and has a 0.6-mL nominal fill volume.

mRNA-1273 is an LNP dispersion of an mRNA encoding the full-length prefusion stabilized S protein of SARS-CoV-2 formulated in LNPs as described for mRNA-1283. mRNA-1273 injection is provided as a sterile liquid for injection, white to off-white dispersion in appearance, at a concentration of 0.2 mg/mL in 20 mM Tris buffer containing 87 mg/mL sucrose and 4.3 mM sodium acetate, at pH 7.5.

### 5.2. Randomization and Blinding

Randomization will be performed using an interactive response technology (IRT). Participants in Part A will be randomized in parallel according to a 1:1:1:1:1:1 ratio (Arm 1: Arm 2: Arm 3: Arm 4: Arm 5: Arm 6). Participants in Part B will be enrolled in the two arms sequentially. Enrollment in both parts of this study will be stratified by age with two age strata: 18-55 years of age and  $\geq$  56 years of age, with at least 20% but not more than 50% of participants 56 years of age or older. All participants, study staff involved in participant assessment, and Sponsor personnel (or its designees) will be blinded to vaccination assignment until the EoS for Part A. Preparation of IP for administration will be conducted on site by an unblinded staff member who has no role in the observation or assessment of study participants. A limited number of Sponsor and/or contract research organization (CRO) personnel will be unblinded to perform Data Safety

Monitoring Board (DSMB) safety data reviews. Additional information regarding unblinding is provided in [Section 5.3.8](#). Part B of the study is open-label and therefore unblinded.

### **5.3. Preparation/Handling/Storage/Accountability**

#### **5.3.1. Study Vaccine Preparation**

Each dose of IP in Part A will be prepared for each participant based on the treatment group.

Each injection will have a volume of 0.25 mL. The vaccines will contain mRNA-1283 at the doses of **CCI** [REDACTED], mRNA-1283.211 at the doses of **CCI** [REDACTED]

[REDACTED], and mRNA-1273 at the dose of **CCI** [REDACTED].

Each dose of IP in Part B will be prepared for each participant based on the treatment group.

Each injection will have a volume of 0.25 mL. The vaccines will contain mRNA-1283.529 at the doses of **CCI** [REDACTED].

Vaccine preparation instructions are detailed in the mRNA-1283-P201 Pharmacy Manual.

#### **5.3.2. Study Vaccine Administration (Part A and Part B)**

Investigational product will be administered as an IM injection into the deltoid muscle on Day 1. Preferably, vaccine should be administered into the nondominant arm.

On Day 1, participants will be monitored for a minimum of 30 minutes after vaccination.

Assessments will include vital sign measurements and monitoring for local or systemic ARs as shown in the SoE ([Table 8](#)).

The study site will be appropriately staffed with individuals with basic cardiopulmonary resuscitation training/certification. Either onsite resuscitation equipment or appropriate protocols for the rapid transport of a participant to a resuscitation area or facility are required.

#### **5.3.3. Study Vaccine Delivery and Receipt**

The Sponsor or designee is responsible for the following:

- Supplying the IP
- Confirming the appropriate labeling of the IP, so that it complies with the legal requirements of the United States

The investigator is responsible for acknowledging the receipt of the IP by a designated staff member at the site, which includes the following:

- Confirming that the IP was received in good condition
- Confirming that the temperature during shipment from the Sponsor to the investigator's designated storage location was appropriate

- Confirming that the Sponsor has authorized the IP for use
- Ensuring the appropriate dose of IP is properly prepared using aseptic technique

Further description of the IP and instructions for the receipt, storage, preparation, administration, accountability, and destruction of IP are described in the mRNA-1283-P201 Pharmacy Manual.

#### **5.3.4. Study Vaccine Packaging and Labeling**

The Sponsor will provide the investigator (via the study site pharmacy) with adequate quantities of IP. Sterile mRNA-1283, mRNA-1283.211, and mRNA-1283.529 (0.4 mg/mL) are packaged in 2R glass vials with a 0.8-mL fill volume. Sterile mRNA-1273 (0.2 mg/mL) is packaged in 10R glass vials with a 6.3-mL fill volume. The IP will have all required labeling per regulations and will be supplied to the pharmacy in an unblinded manner.

The Sponsor or Sponsor's designee will supply the 0.9% sodium chloride injection for use as a diluent for the vaccines. The 0.9% sodium chloride bears a commercial label and does not contain study-specific identification.

The IP will be packaged and labeled in accordance with the standard operating procedures of the Sponsor or of its designee, Code of Federal Regulations (CFR) Title 21 Good Manufacturing Practice guidelines, International Council for Harmonisation (ICH) Good Clinical Practice (GCP) Guidance, guidelines for Quality System Regulations, and applicable regulations.

#### **5.3.5. Study Vaccine Storage**

The mRNA-1283, mRNA-1283.211, and mRNA-1283.529 vaccine candidates must be stored at -90°C to -60°C (-130°F to -76°F) and the mRNA-1273 vaccines must be stored at -25°C to -15°C (-13°F to 5°F) in a secure area with limited access and protected from moisture and light until they are prepared for administration ([Section 5.3.1](#)). The freezer should have automated temperature recording and a 24-hour alert system in place that allows for rapid response in case of refrigerator malfunction. There must be an available backup freezer. The freezer must be connected to a backup generator. In addition, IP accountability study staff are required to keep a temperature log to establish a record of compliance with these storage conditions. The site is responsible for reporting any IP that was not temperature-controlled during shipment or storage. Such IP will be retained for inspection by the monitor and disposed of according to approved methods.

The 0.9% sodium chloride injection (USP) should be stored at 20°C to 25°C (68°F to 77°F) in a restricted access area.

### **5.3.6. Study Vaccine Accountability**

It is the investigator's responsibility that the IP accountability study staff maintain accurate records in an IP accountability log of receipt of all IP, site IP inventory, IP dispensing, IP injections, and return to the Sponsor or alternative disposition of used and unused IP vials.

A site monitor will review the inventory and accountability log during site visits and at the completion of the study. Additional details are found in the mRNA-1283-P201 Pharmacy Manual.

### **5.3.7. Study Vaccine Handling and Disposal**

A site monitor will reconcile the IP inventory during the conduct and at the EoS for compliance. Once fully reconciled at the site at the EoS, the IP should be destroyed on site, if site procedures allow, or returned to a destruction depot per instruction of the Sponsor. Additional details are found in the mRNA-1283-P201 Pharmacy Manual.

### **5.3.8. Unblinding (Part A)**

Part A of this study is an observer-blind study. The investigator, study staff, study participants, site monitors, and Sponsor personnel (or its designees) will be blinded to the IP administered until the EoS for Part A, with the following exceptions:

- Unblinded personnel (of limited number) will be assigned to vaccine accountability procedures and will prepare IP for all participants. These personnel will have no study functions other than study vaccine management, documentation, accountability, preparation, and administration. They will not be involved in participant evaluations and will not reveal the identity of IP to either the participant or the blinded study site personnel involved in the conduct of the study unless this information is necessary in the case of an emergency.
- Unblinded medically qualified study site personnel will administer the IP. They will not be involved in assessments of any study endpoints.
- Unblinded site monitors, not involved in other aspects of monitoring, will be assigned as the IP accountability monitors. They will have responsibilities to ensure that sites are following all proper IP accountability, preparation, and administration procedures.
- The DSMB will review unblinded statistical outputs for ad hoc safety reviews triggered by pause rules, should this occur. See [Section 10.2.11](#) for additional information on DSMB and safety review.
- The pre-identified Sponsor team members will become unblinded to treatment group after primary analysis, but not to individual study participant receipt of study vaccine.

Except in the case of a medical necessity, a participant's treatment assignment should not be unblinded without the approval of the Sponsor. If a participant becomes seriously ill or pregnant during the study, the blind will be broken only if knowledge of the treatment assignment will affect that participant's clinical management. In the event of a medical emergency requiring identification of individual treatment assignment, the investigator will make every attempt to contact the CRO medical monitor to explain the need for unblinding within 24 hours of opening the code. The investigator will be responsible for documenting the time, date, reason for unblinding, and the names of the personnel involved. The investigator (or designee) will have access to unblind participants within IRT. All unblinding instances will be tracked via an audit trail in IRT and documented in the final study report.

#### **5.4. Study Intervention Compliance**

All doses of IP will be administered at the study site under direct observation of medically qualified study staff and appropriately recorded (date and time) in the eCRF. Qualified staff will confirm that the participant has received the entire dose of IP. If a participant does not receive IP or does not receive all of the planned dose, the reason for the missed dose will be recorded. Data will be reconciled with site accountability records to assess compliance.

#### **5.5. Prior and Concomitant Medications (Part A and Part B)**

##### **5.5.1. Prior Medications and Therapies**

Information about prior medications (including any prescription or over-the-counter medications, vaccines, or blood products) taken by the participant within the 28 days before providing informed consent (or as designated in the inclusion/exclusion requirements) will be recorded in the participant's eCRF.

##### **5.5.2. Concomitant Medications and Therapies**

At the study site, study staff must question the participant regarding any medications taken and nonstudy vaccinations received by the participant and record the following information in the eCRF:

- All nonstudy vaccinations administered within the period starting 28 days before the study injection.
- Seasonal influenza vaccine administered for the current influenza season (typically October through April in the Northern Hemisphere).
- All concomitant medications and nonstudy vaccinations taken through 28 days after vaccination. Antipyretics and analgesics taken prophylactically (ie, taken in the

absence of any symptoms in anticipation of an injection reaction) will be recorded as such.

- Any concomitant medications used to prevent or treat COVID-19 or its symptoms.
- Any concomitant medications relevant to or for the treatment of an SAE or an MAAE.
- The participant will be asked in the eDiary if they have taken any antipyretic or analgesic to treat or prevent fever or pain within 7 days after vaccination, including the day of injection. Reported antipyretic or analgesic medications should be recorded in the source document by the study site staff during the post-injection study visits or via other participant interactions (eg, telephone calls).

Concomitant medications (including vaccinations) will be coded using the WHO Drug Dictionary. If a participant takes a prohibited drug therapy, the investigator and the CRO's medical monitor will make a joint decision about continuing or withholding further injection of the participant based on the time the medication was administered, the drug's pharmacology and pharmacokinetics, and whether use of the medication will compromise the participant's safety or interpretation of the data. It is the investigator's responsibility to ensure that details regarding the concomitant medications are adequately recorded in the eCRF.

### **5.5.3. Concomitant Medications and Vaccines that May Lead to the Elimination of a Participant from Per-Protocol Analyses**

The use of the following concomitant medications and/or vaccines will not require withdrawal of the participant from the study but may determine a participant's evaluability in the per-protocol (PP) analysis (analysis sets are described in [Section 8.4](#)):

- Any investigational or nonregistered product (drug or vaccine) other than the IP used during the study period.
- Immunosuppressants or other immune-modifying drugs administered chronically (ie, more than 14 days in total) during the study period. For corticosteroids, this will mean that prednisone  $\geq$  10 mg/day or the equivalent is not permitted. Inhaled, nasal, and topical steroids are allowed.
- Long-acting immune-modifying drugs administered at any time during the study period (eg, infliximab).
- An authorized or licensed vaccine administered during the period from 28 days before through 28 days after vaccination, except for any licensed influenza vaccine that was administered 14 days before or after vaccination.

- Immunoglobulins and/or any blood products administered during the study period.

## **5.6. Intervention After the End of the Study**

Study intervention will not be available to participants after the EoS.

## **6. DELAY OR DISCONTINUATION OF STUDY INTERVENTION AND PARTICIPANT DISCONTINUATION/WITHDRAWAL**

### **6.1. Criteria for Delay of Vaccine Administration**

Body temperature must be measured before vaccination. The following events constitute criteria for delay of injection, and if either of these events occur at the time scheduled for vaccination, the participant may be injected at a later date within the time window specified in the SoE ([Table 8](#)), or the participant may be discontinued from vaccination at the discretion of the investigator ([Section 6.2](#)):

- Acute moderate or severe infection with or without fever at the time of vaccination
- Fever, defined as body temperature  $\geq 38.0^{\circ}\text{C}$  ( $100.4^{\circ}\text{F}$ ) at the time of vaccination

Afebrile participants with minor illnesses can be vaccinated at the discretion of the investigator. Participants with a fever of  $38.0^{\circ}\text{C}$  ( $100.4^{\circ}\text{F}$ ) or higher will be contacted within the time window acceptable for participation and re-evaluated for eligibility. If the investigator determines that the participant's health on the day of vaccination temporarily precludes injection, the visit should be rescheduled within the allowed interval for that visit.

If a participant takes a prohibited drug therapy, an injection could be delayed within the visit window based on the joint decision of the investigator and the CRO's medical monitor ([Section 5.5.3](#)).

### **6.2. Participant Discontinuation/Withdrawal from the Study**

Participants who withdraw or are withdrawn from the study will not be replaced.

Participants can withdraw consent and withdraw from the study at any time, for any reason, without prejudice to further treatment the participant may need to receive. The investigator will request that the participant complete all study procedures pending at the time of withdrawal.

If a participant desires to withdraw from the study because of an AE, the investigator will attempt to obtain agreement to follow up with the participant until the event is considered resolved or stable and will then complete the EoS eCRF.

Information related to the withdrawal will be documented in the eCRF. The investigator will document whether the decision to withdraw a participant from the study was made by the participant or by the investigator, as well as which of the following possible reasons was responsible for withdrawal:

- AE (specify)
- AESI (specify)

- SAE (specify)
- Death
- Lost to follow-up (LTFU)
- Physician decision (specify)
- Pregnancy
- Protocol deviation
- Study terminated by Sponsor
- Withdrawal of consent by participant (specify)
- Other (specify)

Participants who are withdrawn from the study because of AEs (including SAEs and AESIs) must be clearly distinguished from participants who are withdrawn for other reasons.

Investigators will follow up with participants who are withdrawn from the study as a result of an SAE or AE until resolution of the event.

A participant withdrawing from the study may request destruction of any samples taken and not tested, and the investigator must document this in the site study records.

If the participant withdraws consent for disclosure of future information, the Sponsor may retain and continue to use any data collected before such a withdrawal of consent.

The Sponsor will continue to retain and use all research results that have already been collected for the study evaluation, unless the participant has requested destruction of these samples. All biological samples that have already been collected may be retained and analyzed at a later date (or as permitted by local regulations).

### **6.3. Lost to Follow-up**

A participant will be considered LTFU if he or she repeatedly fails to return for scheduled visits without stating an intention to withdraw consent and is unable to be contacted by the study site. The following actions must be taken if a participant fails to return to the clinic for a required study visit:

- The site must attempt to contact the participant and reschedule the missed visit as soon as possible, counsel the participant on the importance of maintaining the assigned visit schedule and ascertain whether the participant wishes to and/or should continue in the study.

- Before a participant is deemed LTFU, the investigator or designee must make every effort to regain contact with the participant (where possible, 3 telephone calls and, if necessary, a certified letter to the participant's last known mailing address or local equivalent methods). These contact attempts (eg, dates of telephone calls and registered letters) should be documented in the participant's medical record.
- A participant who continues to be unreachable or continues to be noncompliant with study visits or procedures will be considered to have withdrawn from the study.
- A participant should not be considered LTFU until due diligence has been completed.

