## 7. STUDY ASSESSMENTS AND PROCEDURES (PART A AND PART B)

Before performing any study procedures, all potential participants will sign an informed consent form (ICF) (as detailed in [Section 10.2.6](#)). Participants will undergo study procedures at the time points specified in the SoE ([Table 8](#)). A participant can also be seen for an unscheduled visit at any time during the study. An unscheduled visit may be prompted by reactogenicity issues, illness visit criteria for COVID-19, or new or ongoing AEs. The site also has the discretion to make reminder telephone calls or send text messages to inform the participant about visits, review eDiary requirements, or follow-up on ongoing or outstanding issues.

The study site staff are responsible for ensuring that participants comply with the allowed study visit windows. If a participant misses a visit, every effort should be made to contact the participant and complete a visit within the defined visit window specified in the SoE ([Table 8](#)). If a participant does not complete a visit within the time window, that visit will be classified as a missed visit and the participant will continue with subsequent scheduled study visits. All safety requirements of the missed visit will be captured and included in the subsequent visit.

In accordance with “FDA Guidance on Conduct of Clinical Trials of Medical Products during COVID-19 Public Health Emergency” ([DHHS 2020](#)), investigators may convert study site visits to home visits or telemedicine visits with the approval of the Sponsor. Such action should be taken to protect the safety and well-being of participants and study site staff or to comply with state or municipal mandates.

General considerations for study assessments and procedures include the following:

- Protocol waivers or exemptions are not allowed. The study procedures and their timing must be followed as presented in the SoE ([Table 8](#)). Adherence to the study design requirements is essential and required for study conduct.
- Immediate safety concerns should be discussed with the Sponsor immediately upon occurrence or awareness to determine if the participant should continue participation in the study.

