## **7.3. Safety Assessments and Procedures**

Safety assessments will include monitoring and recording of the following for each participant, according to the SoE ([Table 8](#)):

- Solicited local and systemic ARs ([Section 7.4.3](#)) that occur during the 7 days following vaccination (ie, the day of injection and 6 subsequent days). Solicited ARs will be recorded daily using eDiaries ([Section 7.3.1](#)).
- Unsolicited AEs observed or reported during the 28 days following vaccination (ie, the day of injection and 27 subsequent days). Unsolicited AEs are defined in [Section 7.4.1](#).
- MAAEs from vaccination on Day 1 through EoS or withdrawal from the study.
- AESIs from vaccination on Day 1 through EoS or withdrawal from the study.
- AEs leading to withdrawal from Day 1 through EoS
- SAEs from vaccination on Day 1 through EoS or withdrawal from the study.
- Vital sign measurements before and after vaccine administration
- Physical examination findings (if performed)
- Details of all pregnancies in female participants will be collected after the start of study treatment and until the end of their participation in the study ([Section 7.4.6](#)).

The incidence and severity of the above events will be monitored by the blinded study team members ([Section 7.5](#)).

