## 6. Statistical Analysis

### 6.1. General Considerations

Please refer to Table 8 in the protocol for Schedule of Events (SoE).

The following follow-up periods for safety analyses and Concomitant Medications will be used:

- Overall follow-up period (throughout the study): from the day of the IP injection (Day 1) to the earliest date of (study completion, discontinuation from the study, or death)
- Up to 28 days follow-up period: from the day of the IP injection (Day 1) to the earliest date of (the day of the IP injection and 27 subsequent days, discontinuation from the study, or death)
- After 28 days follow-up period: from the 28 days after the IP injection to the earliest date of (study completion, discontinuation from the study, or death)
- 7-day follow-up period: from the day of the IP injection (Day 1) to the earliest date of (Day 7 after the IP injection, discontinuation from the study, or death)

**Continuous variables** will be summarized using the following descriptive summary statistics: the number of subjects (n), mean, standard deviation (SD), median, minimum (min), and maximum (max).

**Categorical variables** will be summarized using counts and percentages.

**Baseline value**, unless specified otherwise, is defined as the most recent non-missing measurement (scheduled or unscheduled) collected before the dose of IP in this study.

For the summary statistics of all numerical variables unless otherwise specified, the display precision will follow programming standards. Please see [Appendix A](#) for variable display standards.

When count data are presented, the percentage will be suppressed when the count is zero in order to draw attention to the non-zero counts. A row denoted “Missing” will be included in count tabulations where specified on the shells to account for dropouts and missing values. The denominator for all percentages will be the number of subjects in the treatment group within the analysis set of interest, unless otherwise specified.

**End of Study** (EoS) for the participants is defined as any of completion of the study if the participant has completed all phases of the study including the last scheduled procedure as shown in the SoE (Table 8 in the protocol), discontinuation of study due to any reason, death, and termination of the trial by the Sponsor.

**Pre-booster SARS-CoV-2 status** is determined by using virologic and serologic evidence of SARS-CoV-2 infection on or before Day 1 (pre-booster).

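### Protocol 6.3 can class a reachable participant who misses clinic visits as withdrawn, which ends scheduled SAE, MAAE and AESI collection that the fortnightly eDiary and calls could have continued

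*Protocol*

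**What the plan says.** Protocol 6.3 first defines loss to follow-up narrowly: the person repeatedly misses visits "without stating an intention to withdraw consent and is unable to be contacted by the study site". A later bullet in the same section is wider. Anyone who stays unreachable, or who "continues to be noncompliant with study visits or procedures will be considered to have withdrawn from the study". The two limbs are joined by an alternative, so being reachable does not take a person outside the rule. No number of visits, list of procedures or time limit defines continuing noncompliance.

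Protocol section 7 deals with a visit not completed in its window: "that visit will be classified as a missed visit and the participant will continue with subsequent scheduled study visits". It adds: "All safety requirements of the missed visit will be captured and included in the subsequent visit".

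Protocol 7.3 sets the end of safety collection: "MAAEs from vaccination on Day 1 through EoS or withdrawal from the study", and likewise "SAEs from vaccination on Day 1 through EoS or withdrawal from the study". AESIs have the same limit. Protocol 7.4.12 stops SAE and AESI collection on the last day of participation. SAP 6.1 runs the overall follow-up period from the injection "to the earliest date of (study completion, discontinuation from the study, or death".

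Protocol 7.3.1 and 7.3.2 collect the same events remotely: eDiary questionnaires every two weeks on Days 36 to 162 and 202 to 342, and calls every two weeks on Days 43 to 169 and 209 to 349.

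**The concern.** There is one injection, on Day 1, so withdrawing a participant stops no treatment. It stops only observation. The frequency of SAEs, MAAEs, AESIs and AEs leading to withdrawal from Day 1 to end of study is a primary endpoint in both parts (protocol Tables 1 and 2). It is reported as a number and percentage (protocol Table 7) with the Safety Set as denominator (SAP 6.3.1), and no exposure-adjusted rate is planned.

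A participant who skips the clinic but answers the phone or the eDiary can still supply these data. If 6.3 classes that person as withdrawn, they remain in the denominator and scheduled collection of new events stops. Compared with following the same person to Day 366, the reported count can only stay the same or fall. Follow-up would then be cut short by clinic attendance rather than by loss of contact or withdrawal of consent.

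**Working it through.** The plan states no figure to reproduce. The check is a reading of the sections together, a count of contacts, and an illustration of size.

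**1. Who is caught.** Loss to follow-up in 6.3 requires that contact has failed. Deemed withdrawal in 6.3 requires failed contact or continuing noncompliance. The difference is people who can be contacted, have not withdrawn consent and keep missing visits or procedures.

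**2. What stops and what survives.** Scheduled collection of new SAEs, MAAEs and AESIs stops (7.3, 7.4.12; SAP 6.1). Four things survive:
- a request to complete procedures pending at withdrawal (6.2);
- follow-up to resolution for those withdrawn because of an AE or SAE (6.2);
- follow-up of AEs that are serious, related or caused discontinuation (7.4.11);
- notification of SAEs that the site happens to learn of later and considers related (7.4.12).

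New MAAEs, new AESIs that are not related SAEs, and new unrelated SAEs are not covered.

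**3. Remote contacts available.** Number = (last day − first day)/14 + 1.
- eDiary: (162 − 36)/14 + 1 = 10 and (342 − 202)/14 + 1 = 11.
- Calls: (169 − 43)/14 + 1 = 10 and (349 − 209)/14 + 1 = 11.
- Total 42, plus the Day 8 call, against 5 clinic visits after Day 1 (Days 15, 29, 90, 181 and 366 in protocol Table 8).

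If withdrawal is assumed when the Day 90 window closes (Day 97), the contacts still to come are 5 eDiary and 6 calls in the first block and 11 of each in the second, which is 33 of 42. The observation lost is 366 − 97 = 269 days.

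**4. Illustrative size.** Assumptions, none of them from the documents: a true twelve-month MAAE risk of 30%, a constant hazard, and a share w of the arm withdrawn under this limb, all of whom would otherwise have reported every event remotely. The arm size of 70 is the protocol maximum.

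Risk accrued before withdrawal: r = 1 − 0.70^(d/365), where d is days since injection.
- Withdrawal at Day 29: d = 28, r = 2.7%. Follow-up lost is 337/365 = 92%.
- Withdrawal at Day 97: d = 96, r = 9.0%.

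Reported risk = (1 − w) × 30% + w × r. Participants with an MAAE missed = 70 × w × (30% − r).

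| w | Day 29: reported | Day 29: missed | Day 97: reported | Day 97: missed |
|---|---|---|---|---|
| 3% | 29.2% | 0.6 | 29.4% | 0.4 |
| 5% | 28.6% | 1.0 | 28.9% | 0.7 |
| 10% | 27.3% | 1.9 | 27.9% | 1.5 |

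At Day 29 the relative understatement is about 3% to 9%. For scale, an exact 95% interval for 21 of 70 is 19.6% to 42.1%.

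**The case against.** A reader might infer that 6.3 and section 7 contradict each other outright. They do not. Section 7 concerns one visit missed in its window. Section 6.3 concerns noncompliance that persists after the site has tried to make contact, reschedule and counsel, and to find out whether the person wants to, and should, carry on. The two can be read in sequence. What is left is a tension: no threshold, and no stated route for someone who will answer calls but not attend.

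A reader might infer that 6.2 has no reason code for such cases. It does: protocol deviation, physician decision and other are all listed, though none identifies this group distinctly. Nor does withdrawal end all safety follow-up, as step 2 of the working shows.

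It can also be argued that procedures include the eDiary and calls, so a person who answers them is complying, while a person who refuses them yields no events under any label. The second half is right and limits the fix. The first half does not settle the matter, because the clause is met by noncompliance with visits alone.

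The size is assumed throughout. Withdrawal at Day 29 is close to implausible, since only the Day 15 and Day 29 clinic visits would have come due. No hypotheses are tested, and protocol Table 7 plans no confidence interval for SAEs or MAAEs. The denominator effect follows any dropout, and the SAP makes it partly visible by tabulating discontinuations with reasons (6.2.1) and summarising study duration (6.2.5). This is a fair case for small size. It does not explain why obtainable data should be given up.

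The loss of later titres is a weak argument: people who miss clinic visits give no blood, and the primary time point is Day 29.

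**Conclusion.** The point holds as a gap in the follow-up rule. As written, 6.3 allows a contactable participant who has not withdrawn consent to be removed from scheduled safety follow-up for missing visits, while protocol 7.3.1 and 7.3.2 already provide the means to keep collecting the events. The direction is towards understating the Day 1 to end-of-study safety frequencies.

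The documents do not show how many participants would be affected, and the group is narrow: those who skip the clinic, still respond remotely, and are classed as withdrawn anyway. The 0.6 to 1.9 participants per arm rests on the assumed 30% risk, constant hazard, 3% to 10% share, Day 29 timing and full remote reporting. It should be read as near an upper range, with 0.4 to 1.5 if withdrawal comes at Day 97. That is well inside sampling error for an arm of 70. The case for changing the text is that the loss is avoidable at little cost, not that it is large.

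**What to change.** In protocol 6.3, limit deemed withdrawal to participants who remain unreachable after the listed contact attempts (recorded as lost to follow-up), who withdraw consent, or who decline all further contact, including calls and the eDiary. Add that participants who miss clinic visits but remain contactable and willing stay in eDiary and telephone safety follow-up and may attend any later scheduled visit, in line with section 7. Leave in place the investigator's judgement on whether a participant should continue, with the reason recorded under 6.2. The end points of collection in 7.3, 7.4.12 and SAP 6.1 can then stand unchanged.

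The cost is a sentence or two in one section. The calls and eDiary prompts are already scheduled. The downside is some continued calling of poorly compliant participants, a few of whom will yield little.
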